3.5 Statistical Methods and Analysis

3.5.1 Sample Size Estimation:

This study is designed to provide information on the benefits of the addition of the MetaNeb® System in reducing the incidence of postoperative pulmonary complications (PPCs) in high-risk subjects undergoing high-risk surgical procedures (upper abdominal, thoracic, aortic). The study will be conducted in 2 stages:

- Stage I: To update/confirm the estimate of the current incidence of PPC's with current Standard of Care Practice. Recent published articles suggest incidence rates between 5%-15%, depending on the patient population and type of surgery. This stage of the study will be a retrospective pre-intervention observational period, conducted at 2 - 4 hospitals/sites, with no intervention in the patients' post-surgical

Hill-Rom®	Evaluation of a practice change to include The MetaNeb® System to reduce postoperative pulmonary complications			Page 22 of 31
	CBI	8 September 2016	Rev C	Protocol #: CR-RR2015- 001

management. Data from approximately 200 subjects will be collected. The incidence rate will be calculated, along with a 95% confidence interval.

- Stage II: To assess the impact of the MetaNeb® System on the incidence of PPC's. This stage of the study will be a prospective post-intervention period conducted in the same 2 - 4 hospital sites with an intervention involving use of the MetaNeb® System in addition to Standard of Care Practice.

3.5.2 Statistical Analysis:

- Summary statistics and data listings will be provided.
- Demographic data will be summarized. For continuous type data (e. g. Age), descriptive summary statistics (N, mean, median, standard deviation, min, and max) will be presented. For categorical variables (gender, race, etc.) the number and percent of patients in each category will be provided.

Primary Endpoints:

The incidence of significant postoperative pulmonary complications (as defined in section 3.3) along with 95% confidence interval will be generated. Additionally, the incidence rates will be summarized for various demographic subsets, by surgery type, and for different population subsets. The descriptive summary statistics for the subsets may be presented side-by-side for ease of comparison. The specific subsets to be summarized will be described in a separate document (the statistical analysis plan).

Secondary Endpoints:

The secondary endpoints as listed in section 3.3 will be summarized with descriptive summary statistics appropriate for continuous or categorical data, depending on the outcome being summarized:

1. Requirement for invasive mechanical ventilation for more than 48 hours.
2. Requirement for respiratory support for more than 48 hours
3. Length of ICU stay (ILOS)
4. Length of hospital stay (HLOS)
5. Time on mechanical ventilation
6. Readmission to ICU
7. Readmission to hospital

Hill-Rom®	Evaluation of a practice change to include The MetaNeb® System to reduce postoperative pulmonary complications	Page 23 of 31
CBI	8 September 2016	Rev C

Stage I and Stage II results will be compared for the purpose of identifying any statistical associations that can be attributed to use of The MetaNeb® System.

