Number of Subjects:	The sample size will be approximately 400 patients, 200 in the retrospective STANDARD THERAPY group and 200 in the prospective CHANGE IN PRACTICE group.		
Study Population:	The study population consists of adult post-surgical patients who have undergone thoracic, aortic or upper abdominal surgery who are at high risk for PPCs.		
Inclusion/Exclusion Criteria:	
Inclusion Criteria:
 
Patients who meet all of the following criteria will be included in the study:
 
• Age \geq 18 years• Post-thoracic, -upper abdominal or -aortic surgery• Open surgical procedure• Incision at or above the umbilicus• High risk defined by:
• Documented ASA class \geq 3 
OR
 
• Documented ASA class 2 AND One or more of the following:
• Current smoker or smoking history within past 6 months• History of COPD• Documented obesity and/or BMI \geq 30 kg/m²• Age \geq 75 
Exclusion Criteria:
 
Patients who meet any of the following criteria will be excluded (or will be exited) from the study:
 
• Contraindication to Continuous High Frequency Oscillation (CHFO) therapy (e.g. untreated tension pneumothorax)• Minimally invasive, or “... scopic” procedure.• Spinal surgery involving a posterior approach• Surgery for organ transplant• Chronic invasive positive pressure ventilation (PPV)		

Statistical Methods:	
Descriptive summary statistics will be provided for demographics, the primary and secondary endpoints. Continuous data will be summarized with N, mean, median, standard deviation, min, and max. Categorical data will be summarized with the number and percent of patients in each category. Time to event data (ex. Time to readmission) will be summarized with methods appropriate for survival data including a Kaplan-Meier plot.
 
Ninety-five percent (95%) confidence interval will be computed for the primary endpoint, the incidence of significant postoperative pulmonary complications. Incidence rates for various demographic subsets, surgery types, and different population subsets may be presented as outlined in the statistical analysis plan document, to be published prior to study completion. Stage I and Stage II incident rates will be compared for the purpose of identifying any statistical associations that can be attributed to use of The MetaNeb® System.
		

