3.0 Study Design

3.1 Overview of Study Design

3.1.1 Design:

This is a non-randomized facility level pre-post intervention study conducted in two stages for the primary purpose of evaluating the effect of The MetaNeb® System on postoperative pulmonary complications in high risk patients undergoing thoracic and

Hill-Rom®	Evaluation of a practice change to include The MetaNeb® System to reduce postoperative pulmonary complications	Page 13 of 31
CBI	8 September 2016	Rev C Protocol #: CR-RR2015-001

abdominal surgeries. The study will be conducted in two to four (2-4) tertiary academic medical facilities in the US that have not previously used The MetaNeb® System in post-thoracic, post-aortic, or post-upper abdominal surgery patients. After assessing outcomes during a baseline period, therapy with The MetaNeb® System will be introduced and incorporated into the respiratory care treatment regimens and outcomes will be assessed after the change in practice.

3.1.2 Procedure:

In Stage I of the study, a retrospective review of medical records for post-surgical patients, who received STANDARD THERAPY as defined by current hospital and Respiratory Care department policies and procedures. This will be a retrospective data collection only.

The purpose of study Stage I is to estimate the incidence of postoperative pulmonary complications in post-surgical patients receiving standard of care per hospital and Respiratory Care department procedures and policies. Data collected in Stage I will include data from the medical records of 200 randomly selected, eligible patients treated during the year prior to the CHANGE IN PRACTICE. This allows for inclusion of patients from the seasonally consistent time period as well as those from most recent time period, during which care practices are most similar.

In Stage II, a CHANGE IN PRACTICE will be made and patients will receive standard care with the addition of therapy with The MetaNeb® System. Other standard airway clearance and lung expansion therapies typically delivered by Respiratory Therapy will not be delivered during Stage II. During Stage II, data from approximately 200 patients will be collected from the medical records across the 3 sites.

Demographic, clinical & outcome data will be collected for eligible patients during the two stages of the study. Study staff will collect data from the medical records, following a protocol determined schedule.

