### **3 STUDY DESIGN**

This is a non-randomized facility level pre-post intervention study conducted in two stages for the primary purpose of evaluating the effect of The MetaNeb® System on postoperative pulmonary complications in high risk patients undergoing thoracic and abdominal surgeries. The study will be conducted in two to four (2-4) tertiary academic medical facilities in the US that have not previously used The MetaNeb® System in post-thoracic, post-aortic, or post-upper abdominal surgery patients. After assessing outcomes during a baseline period, therapy with The MetaNeb® System will be introduced and incorporated into the respiratory care treatment regimens and outcomes will be assessed after the change in practice.

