### **6.3 Analysis Methods – Primary and Secondary Endpoints**

#### **Primary Endpoint— Proportion of subjects who have a postoperative pulmonary complication**

The proportion of subjects who have a PPC within 7 days of post-surgery hospital admission will be presented with 95% confidence intervals.

Incidence of each of the 4 components that contribute to the primary endpoints, will also be presented.

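### The protocol says stage differences can be attributed to the device, but a sequential pre-post design can support only an association with the change in practice

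*Protocol*

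**What the plan says.** Protocol section 3.5.2 closes by stating the purpose of the between-stage comparison: "for the purpose of identifying any statistical associations that can be attributed to use of The MetaNeb® System". The statistical methods entry of the synopsis applies the same purpose to the primary endpoint: "Stage I and Stage II incident rates will be compared for the purpose of identifying any statistical associations", followed by the same attribution clause. Section 3.5.1 describes Stage II as assessing the device's impact on complication incidence.

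The design is stated openly in protocol section 3.1.1: "This is a non-randomized facility level pre-post intervention study conducted in two stages". Section 3.5.1 describes Stage II as a "prospective post-intervention period conducted in the same 2 - 4 hospital sites". SAP section 1 adds that Stage II begins only once Stage I data have been gathered and analysed.

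One provision bears on time. Protocol section 3.1.2 and SAP section 1 draw the 200 Stage I patients at random from the year before the change, so that season is matched and care practices are as similar as possible.

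For the primary endpoint, SAP section 6.3 plans: "The proportion of subjects who have a PPC within 7 days of post-surgery hospital admission will be presented with 95% confidence intervals". It also reports the four components. It names no between-stage test, model or display by calendar time.

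**The concern.** Each hospital changes practice once, and all hospitals stand on the same side of the change within each stage. Anything else that differs between the periods falls into the same contrast as the device: extubation habits, oxygen weaning, staffing, or the extra attention of a prospective study. The endpoint is open to this. Two of its four components depend on ventilation, or on NIV, CPAP or oxygen support, continuing past hour 24 (protocol section 3.3), and ordinary changes in practice can move these.

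At stake is what the trial may conclude. With the attribution clause in the protocol, a lower Stage II rate could be reported as an effect of the device when the design shows only that it coincided with the change in practice.

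**Working it through.** **Step 1: is there any concurrent comparator?** Stage I is retrospective and ends before the change. Stage II is prospective, at the same hospitals, and starts after Stage I has been analysed. Neither document keeps a site or patient group on standard therapy during Stage II. Stage and exposure are therefore the same variable, and the expected stage difference equals the device effect plus all drift between the periods.

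**Step 2: how much could drift matter?** The plan has no figure of its own to reproduce: SAP section 5 states that no formal sample size determination was made. Inputs from the documents:
- about 200 patients per stage (synopsis)
- complication incidence of 5% to 15% (protocol section 3.5.1)
- two-sided 5% tests (SAP section 6)

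Assumptions, not in the documents:
- the device has no effect
- incidence falls by 10% or 20% in relative terms between stages
- the comparison is a simple two-proportion z-test

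With d = p1 − p2 and SE = sqrt(p1(1−p1)/200 + p2(1−p2)/200), the chance of a significant result favouring the device is P(Z > 1.96 − d/SE).

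| Stage I → Stage II | d | SE | d/SE | Chance of false benefit |
|---|---|---|---|---|
| no drift | 0 | – | 0 | 2.5% |
| 5% → 4.5% | 0.005 | 0.0213 | 0.24 | 4.2% |
| 5% → 4% | 0.010 | 0.0207 | 0.48 | 7.0% |
| 10% → 9% | 0.010 | 0.0293 | 0.34 | 5.3% |
| 10% → 8% | 0.020 | 0.0286 | 0.70 | 10.4% |
| 15% → 13.5% | 0.015 | 0.0350 | 0.43 | 6.3% |
| 15% → 12% | 0.030 | 0.0341 | 0.88 | 14.0% |

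A pooled standard error changes only the last entry, to 13.9%. Drift also works the other way: a true 3-point benefit set against a 3-point background rise gives an expected stage difference of zero.

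**Step 3: could the trial's own dates settle the matter?** Two analyses suggest themselves.

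*A trend test within Stage I.* With admissions spread evenly over one year, the SE of the log-odds slope is 1/sqrt(200 × p(1−p)/12). This is 0.82 per year at p = 0.10 and 0.69 at p = 0.15. A fall from 10% to 8% over a year is 0.245 log-odds, so z = 0.245/0.82 = 0.30 and two-sided power is about 6%. A fall from 15% to 12% is 0.258, so z = 0.38 and power is about 7%.

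*A linear calendar-time term beside the stage term.* The variance of the stage effect is multiplied by 1/(1−r²), where r is the correlation of stage with date. Assume a 12-month Stage I, a 6- to 12-month Stage II, and 200 evenly spaced dates in each. The factor is about 3.7 to 4.0 with no gap between stages and about 5.6 to 5.8 with a 3-month gap. For example, take a 3-month gap and a 6-month Stage II. The stage midpoints are then 1.0 year apart, the between-stage variance of time is 1.0²/4 = 0.25, and the within-stage variance is (1/12 + 0.25/12)/2 = 0.052. The factor is 1 + 0.25/0.052 = 5.8. The 200 per stage then carry the information of about 34 to 54 per stage. Power for a fall from 15% to 7.5% drops from 66% to about 16–23%.

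The true interval between stages is not fixed by the documents. The synopsis anchors the Stage I year to study initiation, and section 3.1.2 anchors it to the change in practice. These should be reconciled.

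**The case against.** The strongest reply is that the plan is open about its design and modest in much of its language. Both documents call the study non-randomized and pre-post. The SAP objectives in section 2.1 are only to estimate incidence in each stage. The disputed clause speaks of statistical associations and states the purpose of a comparison; it is not a rule for drawing conclusions. Stage I was deliberately drawn from the preceding year to handle season and recency. All of this stands, and it limits the point to one of wording. It does not remove it, because the clause is causal in meaning and the choice of window neither estimates nor adjusts for a trend.

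A reader might infer that complications were already declining and that the trial would credit this decline to the device. The documents do not support that. They report no trend in either direction, and the drift sizes above are assumptions. The test is assumed too, since SAP section 6.3 names no between-stage comparison. That is a separate and more basic gap.

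A reader might also infer that a trend analysis would cure the problem. It would not. The Stage I trend test has almost no power against the drifts considered, and the calendar-time model gives up most of the information. Neither can separate the device from a step that begins with Stage II, such as the attention of being studied. A flat quarterly plot could reassure falsely.

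**Conclusion.** The point holds as a correction of the stated claim. The synopsis and protocol section 3.5.2 give the stage comparison a property that the design lacks. What it can show is an association with the change in practice at these hospitals. This conclusion follows from the design alone and depends on no drift figure.

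The size is hypothetical. Under the assumptions in Step 2, the 2.5% chance of a false benefit becomes 4.2% to 6.3% for a 10% relative fall and 7.0% to 14.0% for a 20% fall, across the protocol's own baseline range. Upward drift of similar size would mask a real benefit. A pre-post design remains a legitimate choice; the change should be made because the claim goes beyond it.

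**What to change.** In the synopsis and in protocol section 3.5.2, replace the attribution clause so that the stages are compared to identify differences that *are associated with the change in practice*. Add one sentence: *Secular trend and other period effects cannot be separated from the effect of the device in this design.*

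Optionally, add to SAP section 6.3 a descriptive table or plot of complication incidence by calendar quarter of post-surgical admission across both stages. Admission dates are already collected. Label it exploratory and note that a flat plot does not rule out drift: at about 50 Stage I patients per quarter and 10% incidence, the 95% half-width is 1.96 × sqrt(0.10 × 0.90/50) = 8.3 percentage points.

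A Stage I trend test and a calendar-time model are best left out. If either is included, label it exploratory and state the roughly 6–7% power and the 3.7- to 5.8-fold variance inflation, with the assumptions behind them. The model would also need a between-stage comparison, which the SAP does not yet specify.

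The cost is two sentences reworded, one added and, if wanted, one figure. The downside is a more modest stated claim.

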4.0 General Study Information

4.1 Technical Support

Technical product support will be performed by Hill-Rom following routine service practices (contact details will be provided).

4.2 Record Retention

Records must be maintained for a period of up to three years after the latter of the following dates: the date the study is completed/terminated, or the date of the last regulatory approval. The Investigators or Institutions shall notify the Sponsor at least thirty (30) days prior to any planned destruction of records from this study.

All records will be kept confidential and the patient's name will not be released at any time. Code numbers will be used to de-identify patient information on the CRFs and other study-related documents.

5.0 Study Procedures

5.1 Informed Consent:

A waiver of informed consent will be requested for patients enrolled in the study in Stage I (retrospective review of data). Informed consent must be obtained from all subjects in Stage II prior to participation as per Federal Regulations and/or the qualifying Institutional Review Board (IRB). A blank copy of the IRB-approved form must be kept on-site and by the sponsor. The signed original for each subject must be kept in the study files.

5.2 Complaints and Adverse Events Reporting

During the study, any adverse device effect, device-related complaint or allegation of injury (of any type) must be reported to the Sponsor within 24 hours. Please contact

PI

Hill-Rom®	Evaluation of a practice change to include The MetaNeb® System to reduce postoperative pulmonary complications	Page 24 of 31
CBI	8 September 2016	Rev C Protocol #: CR-RR2015-001

A complaint is defined as any written, electronic or verbal communication that alleges deficiencies related to the identity, design, quality, durability, reliability, safety, effectiveness or performance of the device. A serious injury is defined as an injury or illness that is life-threatening; results in permanent impairment of a body function or permanent damage to a body structure; or necessitates medical or surgical intervention to preclude permanent impairment of a body function or permanent damage to a body structure.

Any device complaint and/or allegation of injury shall be reviewed, evaluated, and investigated by Hill-Rom Post Market Surveillance and reported to the appropriate Health Authority per current regulations. The Investigators are responsible for informing the Institutional Review Boards, as per their guidelines.

5.3 Deviations from the Study Protocol

A change (other than administrative) to any part of the study protocol must be mutually agreed upon by the Sponsor and the Investigator(s). The Investigator(s) will then submit an amendment to his/her/their institution's local IRB. Until the new protocol is approved, new patients will be included under the current protocol.

5.4 Materials Provided by the Sponsor

The Sponsor will supply all The MetaNeb® System devices to the institutions.

6.0 Investigator and Sponsor Responsibilities

6.1 Investigator's Responsibilities

The Investigator will comply with Good Clinical Practices (GCPs) and applicable regulatory requirements, as itemized below.

- The Investigator should be familiar with the appropriate use of The MetaNeb® System Device and any other information provided by the Sponsor.
- The Investigator should provide adequate staff to conduct and complete the study within the agreed study time period. The Investigator should ensure that all persons assisting with the study are adequately informed about the protocol, The MetaNeb® System Device and their study related duties.

Hill-Rom®	Evaluation of a practice change to include The MetaNeb® System to reduce postoperative pulmonary complications	Page 25 of 31
CBI	8 September 2016	Rev C

- A qualified physician delegated as an investigator or sub-investigator will be responsible for all study related duties and functions. During a patients' participation, the Investigator/Institution should ensure that adequate medical care is provided to the patient for any adverse event.
- The Investigator should have written and dated approval from the IRB for the protocol, IC forms or waiver of informed consent, HIPAA authorization, patient recruitment procedures and any other written information for the conduct of the study and/or to be provided to patients.
- The Investigator/Institution should conduct the study in compliance with the protocol agreed to by the Sponsor. The Investigator should sign the protocol or alternative contract to confirm agreement. The Investigator should not implement any deviation or changes to the protocol without agreement with the Sponsor and prior review and agreement from the IRB, unless the deviation or change is to eliminate an immediate hazard to study patients.
- The Investigator/Institution is responsible for all MetaNeb® System Devices that are placed with the Investigator/Institution. When it is allowed, the Investigator may assign Device accountability to another appropriate individual. The Investigator or responsible individual shall maintain records of the Device delivery to the site, inventory at the site, the use by each patient, and the return to the Sponsor of unused Device or equipment. The MetaNeb® System Device should be stored as specified by the Sponsor and applicable regulatory requirements. The Investigator should ensure that the individual Device is demonstrated and/or used in accordance with the approved protocol. If appropriate and applicable, the Investigator or designee should explain the correct use of The MetaNeb® System Device to each patient.
- In obtaining and documenting informed consent (unless waived), the Investigator should comply with the applicable regulatory requirements and should adhere to GCP and the ethical principles that have their origin in the Declaration of Helsinki.
- The Investigator, per Title 21 Code of Federal Regulations Part 54, should disclose any financial interests that could affect the reliability of the data.
- The Investigator should ensure the accuracy, completeness, legibility and timeliness of the data reported to the Sponsor in the CRFs and required reports.

Hill-Rom®	Evaluation of a practice change to include The MetaNeb® System to reduce postoperative pulmonary complications	Page 26 of 31
CBI	8 September 2016	Rev C Protocol #: CR-RR2015- 001

- The Investigator should maintain the study documents as required by the applicable regulatory requirements. Records must be maintained for a period of three years after the latter of the following dates: the date the study is completed/terminated or the date of the last regulatory approval based on the study data. The Investigator or Institution shall notify the Sponsor at least thirty (30) days prior to any planned destruction of records from this study.
- The Investigator should submit written summaries of the status of the study to the IRB annually, or as requested by the IRB, and upon completion of the Study.
- All serious adverse device effects should be reported immediately to the Sponsor, per the local IRB's reporting policy at that site. The initial reports should be followed by more detailed reports if more information becomes available. If the study is terminated prematurely or suspended for any reason, the Investigator should promptly inform the study patients and ensure appropriate therapy and follow-up is scheduled or documented for each patient.

